3.1.1.2. Participants Free of Panic Attacks

A participant is considered to be panic free within a two-week interval if during each two-week interval, there is a minimum of 12 days of the eDiary completed and there is no presence of panic attacks associated with 4 symptoms as specified in DSM-5-TR. The outcome for participants who do not report a panic attack associated with four symptoms but have fewer than 12 completed eDiary days, will be considered missing for efficacy analysis.

A modified definition will be used in supportive analyses. Under the modified definition, a participant is considered to be panic free within a two-week interval if during each two-week interval, there are no missing eDiary days and there is no presence of panic attacks associated with 4 symptoms as specified in DSM-5-TR. The outcome for participants who do not report a panic attack associated with 4 symptoms but have missing eDiary days, will be considered missing for efficacy analysis.

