### 5.1. Inclusion Criteria

Individuals are eligible for participation in this trial only if all of the following criteria apply:

1.	Male and female participants, ages 18-65 years, inclusive, at the time of Screening.
2.	Primary diagnosis of panic disorder based on the DSM-5-TR criteria (present for at least 6 months prior to the Screening Visit) and confirmed by the MINI; additional primary diagnosis of agoraphobia is allowed and secondary diagnosis of GAD and/or SAD is allowed.
3.	Participant has had a minimum of 8 panic attacks, with no week free of panic attacks, in the month prior to the Screening Visit. In the 14 days preceding the Baseline Visit, the participant must have had at least 4 panic attacks and no week free of panic attacks. Note: Participant must complete a minimum of 11 eDiary day entries in the 14 days preceding the Baseline Visit.
4.	Participants with a PDSS total score $\geq 12$ at the Screening and Baseline Visits
5.	Body mass index of 17.5 to 40.0 kg/m  and a total body weight >48 kg at Screening.
6.	A female participant of childbearing potential who is sexually active with a nonsterilized male partner must agree to use a highly effective method of contraception (defined in Section 10.4.1.2 ) from signing of informed consent throughout the duration of the trial until the last dose of IMP and for an additional 33 days after the last dose. A male participant with a pregnant or a nonpregnant partner of childbearing potential must agree to use a condom during treatment and until the last dose of IMP and for an additional 93 days. In addition, male participants should not donate sperm for a minimum of 93 days following last dose of IMP.
7.	Capable of giving signed informed consent, which includes compliance with the requirements and restrictions listed in the ICF and in the trial protocol.
8.	Ability, in the opinion of the investigator, to understand the nature of the trial and comply with protocol requirements, including the prescribed dosage regimens, scheduled visits, laboratory tests, and other trial procedures.

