1.2. Sample Size Considerations

A sample size of 114 participants per group (total of 228 participants) will provide at least 80% power to detect a difference of approximately 20% in proportion of participants (e.g., 60% of darigabat group versus 40% of placebo group) free of panic attacks at Week 14 at $\alpha=0.05$ (2-sided).

Two-hundred forty-six participants will be randomized to account for 18 participants whose panic attack assessments were made prior to implementation of protocol eDiary requirements (i.e., assessments recorded contemporaneous to the day being assessed [minimizing any potential recall bias] and records of the presence as well as the absence of each DSM-5-TR panic attack symptom associated with a given panic attack [distinguishing between missing data and the absence of a specific symptom]).

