3.1.1.3. Derivation of Proportion of Participants Free of Panic Attacks

The proportion of participants free of panic attacks is derived as the number of participants who do not experience any panic attacks (defined by DSM-5-TR) over a two-week interval divided by the total number of participants in the treatment group. Calculations will be derived initially for weeks where at least 12 days reported on a diary per two-week interval (>80%). Participants with fewer than 12 days of completed eDiary entries who have not reported a panic attack will be considered missing from this analysis. Calculations will also be derived for weeks where all 14 days were reported on a diary per two-week interval (100%). Participants with fewer than 14 days of completed eDiary entries who have not reported a panic attack will be considered missing from this analysis.

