5.11.3. Sensitivity Analyses

A sensitivity analysis using Fisher's exact test and 95% exact CI about the difference in treatment groups will be performed to assess the robustness of the conclusion from the logistic regression and the impact of potential use of a structured covariance matrix on the estimation of treatment effect.

Participants will be assessed based on the final two weeks of treatment in the Maintenance Period. Those with less than 12 eDiary days and no reported panic attacks will be imputed as missing.

Additional sensitivity analysis will include the model-based analysis described in [Section 5.11.2](#) conducted using all participants regardless of panic attack eDiary version used.

Lastly, two sensitivity analyses will be performed using modified definitions of the efficacy endpoint, free of panic attacks. Under the first modified definition, a participant is considered to be panic free within a two-week interval if during each two-week interval, there are no missing eDiary days and there is no presence of panic attacks associated with 4 symptoms as specified in DSM-5-TR. The second definition will require 10 or more eDiary days without a reported panic attack (per DSM-5-TR). The outcome for participants who do not report a panic attack associated (per DSM-5-TR) but have missing eDiary days, will be considered missing for efficacy analysis. Analysis using the model-based approach described in [Section 5.11.2](#) will be performed using the 14/14 eDiary day definition and the Fisher's exact test will be performed using the both modified definitions.

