9.4. Programming Conventions

- Page orientation, margins, and fonts: Summary tables, listings, and figures will appear in landscape orientation. There should be a 1.0” boundary on the left and right edges. The top and bottom margins are 1.0” for tables and listings but may vary for figures. Output should be printed in Courier New with a point size of 8.
- Identification of analysis population: Every summary table, listing, and figure will clearly specify the analysis population being summarized/listed. Listings will be prepared for all participants randomized.
- Group headers: In the summary tables, the group headers will identify the within-group sample size for the indicated analysis population. Of note, the header’s sample size does not necessarily equal the number of participants actually summarized within any given summary module; some participants in the analysis population may have missing values and thus may not be summarized.
- Suppression of percentages corresponding to null categories: When count data are presented as category frequencies and corresponding percentages, the percent should be suppressed when the count is zero in order to draw attention to the non-zero counts.
- Presentation of sample sizes: Summary modules should indicate, in one way or another, the number of participants actually contributing to the summary statistics presented in any given summary module. As mentioned above, this may be less than the number of participants in the analysis population.
 - ◆ In the quantitative modules describing continuous variables (and thus presenting sample size, means, and standard deviations), the sample size should be the number of non-missing observations
 - ◆ For categorical variables that are presented in frequency tables, the module should present the total count in addition to the count in each category. Percentages should be calculated using this total as the denominator, and the percentage corresponding to the sum itself (that is, 100%) should be presented so as to indicate clearly to a reviewer the method of calculation.
- Sorting: Listings will be sorted by treatment, participant number and date, if applicable. If a listing is sorted in a different manner, it will be indicated on the listing shells.

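### Short diaries are set to missing only when no attack was recorded, which removes apparent successes and biases the odds ratio against the arm with lower diary completion

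*SAP*

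**What the plan says.** A two-week interval counts as panic free if "there is a minimum of 12 days of the eDiary completed and there is no presence of panic attacks associated with 4 symptoms" (SAP 3.1.1.2). The same section continues: "participants who do not report a panic attack associated with four symptoms but have fewer than 12 completed eDiary days, will be considered missing". No sentence says what happens to a short diary that contains an attack. Such a participant cannot be panic free and is outside the missing rule, so by implication is a failure. SAP 3.1.1.3 and 5.11.3 repeat the rule, so the primary model and Fisher's test share it. SAP 6 lists it among the additions to the protocol's analysis.

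SAP 3.1.1.3 forms the proportion as a count "divided by the total number of participants in the treatment group", but also treats short no-attack diaries as missing from the analysis. SAP 9.4 says of frequency tables: "Percentages should be calculated using this total as the denominator", where the total is the number of participants actually summarised.

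SAP 5.11.3 adds two modified definitions. One requires all 14 days. For the other, "The second definition will require 10 or more eDiary days without a reported panic attack (per DSM-5-TR". The next sentence says that participants with no attack "but have missing eDiary days, will be considered missing for efficacy analysis".

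**The concern.** A participant with 11 clean days is dropped. A participant with 11 days, one of them with an attack, is kept as a failure. Short diaries thus remove apparent successes and leave failures in place. If the arms complete their diaries at different rates, successes are removed at different rates, and the odds ratio moves away from its true value even with no drug effect.

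Unequal completion is plausible. Protocol 4.3.1 lists bradyphrenia, somnolence and disturbance in attention among the adverse events more common than on placebo at the trial dose. No planned analysis imputes the dropped cases or applies the cut-off to both outcomes. SAP 5.9 only describes compliance by arm.

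**Working it through.** **Benchmark from the plan.** SAP 1.2 gives 114 per group, 60% versus 40%, two-sided 0.05, at least 80% power. The normal approximation gives 86.0% and Fisher's test 83.8%, so the statement is reproduced. The design odds ratio is (0.60/0.40)/(0.40/0.60) = 2.25.

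**Inputs.** The 12-of-14 cut-off is from SAP 3.1.1.2. Daily completion *c* is an assumption, varied from 80% to 95%. The true panic-free proportion *p* is 0.40 in both arms (no drug effect).

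**Step 1: chance of reaching 12 days.** With independent days, q = Σ C(14,k) c^k (1−c)^(14−k) for k = 12 to 14. At c = 0.90, q = 0.257 + 0.356 + 0.229 = 0.842.

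**Step 2: what the rule reports.** If failures have enough attacks for at least one to be recorded, successes survive with probability q and failures always survive. The observed proportion is pq/(pq + 1 − p) and the observed odds are pq/(1 − p).

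| Daily completion | q | Observed proportion (true 40%) |
|---|---|---|
| 95% | 0.970 | 39.3% |
| 90% | 0.842 | 35.9% |
| 85% | 0.648 | 30.2% |
| 80% | 0.448 | 23.0% |

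**Step 3: false odds ratio.** With equal *p*, (1 − p) cancels and the odds ratio is q_A/q_B, whatever *p* is. Equal completion gives 1.00. False-positive rates were simulated at 114 per arm (Wald test, endpoint period only).

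| Completion, A vs B | False odds ratio | False positives |
|---|---|---|
| 95% vs 90% | 0.970/0.842 = 1.15 | 8.0% |
| 90% vs 85% | 0.842/0.648 = 1.30 | 14.1% |
| 95% vs 85% | 0.970/0.648 = 1.50 | 27.8% |
| 90% vs 80% | 0.842/0.448 = 1.88 | 50.1% |

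**Step 4: weaker assumptions.** Clustering missed days within persons (intraclass correlation 0.2) gives 1.14 to 1.17 for a 5-point gap (7 to 8% false positives) and 1.33 to 1.39 for a 10-point gap (16 to 19%). If every failure has only one attack day, which may fall on a missed day, a 5-point gap gives 1.05 to 1.20 with independent days. Combining both assumptions (run at a true 60%), a 10-point gap gives 1.17 to 1.22.

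Without any model for days, if a share *m* of participants in each arm has a short diary regardless of outcome, the odds ratio is (1 − m_A)/(1 − m_B). For 10% vs 15% it is 0.90/0.85 = 1.06. For 10% vs 25% it is 0.90/0.75 = 1.20.

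**Step 5: direction under the design effect.** With a true 60% vs 40% and lower completion on darigabat, 85% vs 90% gives 2.25 × 0.648/0.842 = 1.73, and 80% vs 90% gives 2.25 × 0.448/0.842 = 1.20.

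**Step 6: the sensitivity definitions (all failures seen).** Requiring 14 days, the false odds ratio is 0.488/0.229 = 2.13 (95% vs 90%) and 0.229/0.103 = 2.23 (90% vs 85%, from unrounded values). Requiring 10 days, it is 1.01 and 1.04, and 0.991/0.870 = 1.14 for 90% vs 80%. The 10-day version is the only planned analysis that nearly removes the bias. The sentence after it sets no-attack participants with any missing day to missing. Taken literally, that is the 14-day rule again. It is also planned for Fisher's test only and is absent from the SAP 5.13 summary.

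**The case against.** **The rule has a rationale.** One recorded attack settles the outcome, while an incomplete clean diary is unknown. This stands, and it is why applying the 12-day cut-off to both outcomes should not become the primary rule: it discards certain failures. If attack days are recorded 15% less often (an assumption, true 45% in both arms), that symmetric rule gives 49.6 to 53.7% and odds ratios of 0.91 to 0.94. Under the same assumption the SAP rule at 95% completion gives 46.9%, so the downward bias is not universal.

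**The size is assumed.** This also stands. No completion rate is given, the diary is reviewed at every on-treatment visit and call (Protocol 1.3), and entry screens out participants who miss more than 3 of 14 days. A 10-point gap may not occur.

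**The 10-day wording is only loose.** SAP 5.11.3 speaks of two analyses and names the 14-day definition separately, so the intent was probably distinct. A programmer must still follow the sentence as written or depart from it.

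**Stronger readings that the documents do not support.** A reader might infer that the rule creates a false benefit for darigabat. The adverse-event profile points the other way, and nothing suggests better completion on darigabat. A reader might see a conflict with inclusion criterion 3, "Participant must complete a minimum of 11 eDiary day entries in the 14 days preceding the Baseline Visit". That is an eligibility threshold, not an outcome definition. A reader might also infer that SAP 3.1.1.3 turns missing into failure in the primary odds ratio. Its own later sentences and 9.4 largely override that denominator, and the odds ratio comes from a model (5.11.2) that does not use it.

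**Conclusion.** The concern holds, with a conditional size. Missingness depends on the outcome in both the primary model and Fisher's test. With no drug effect, a 5-point gap in daily completion gives a false odds ratio of about 1.05 to 1.30. A 10-point gap gives about 1.3 to 1.9 depending on clustering, or about 1.2 if in addition every failure has a single attack day. All are below the design value of 2.25. With equal completion only the proportions are affected.

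These figures rest on assumed completion rates, on completion unrelated to attacks, and on the endpoint period alone. The repeated-measures model was not simulated. The final sample will be smaller than planned, which lowers the false-positive rates but not the bias: 10% vs 25% short diaries gives 10.0% at 114 per arm and 6.8% at 50. SAP 6 calls efficacy exploratory and SAP 5.4 drops multiplicity control, so no confirmatory claim depends on this. It should be fixed because the estimate is what the trial will report.

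**What to change.** Before unblinding, by SAP wording and programming only:

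1. Keep a recorded attack as a failure. For short no-attack diaries, multiply impute the unrecorded days from the participant's recorded days, arm and baseline frequency, then classify the interval. Report bounds with all such cases as failures and all as successes and, for the odds ratio, crossed between arms. If this is not made primary, add it as a sensitivity analysis. Use the symmetric 12-day rule only as a further sensitivity analysis. Counting these cases as failures is a bound and not a repair: at a true 40% in both arms it gives odds ratios of 1.25 (95% vs 90%) and 1.45 (90% vs 85%).
2. Reword the 10-day definition in 5.11.3: *at least 10 completed days and no attack on any recorded day; no recorded attack and fewer than 10 completed days is missing*. List it in 5.13.
3. In 3.1.1.3, state that the denominator is participants with a non-missing outcome.

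The cost is a little more analysis work and reliance on an imputation model. No new data are needed. If unblinding has already happened, report these as documented additions under SAP 6.

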3.1.1.3. Derivation of Proportion of Participants Free of Panic Attacks

The proportion of participants free of panic attacks is derived as the number of participants who do not experience any panic attacks (defined by DSM-5-TR) over a two-week interval divided by the total number of participants in the treatment group. Calculations will be derived initially for weeks where at least 12 days reported on a diary per two-week interval (>80%). Participants with fewer than 12 days of completed eDiary entries who have not reported a panic attack will be considered missing from this analysis. Calculations will also be derived for weeks where all 14 days were reported on a diary per two-week interval (100%). Participants with fewer than 14 days of completed eDiary entries who have not reported a panic attack will be considered missing from this analysis.

3.1.2. Panic Disorder Severity Scale

The Panic Disorder Severity Scale (PDSS) (Shear et al, 1997) is a 7-item, clinician-administered measure of panic disorder severity that covers multiple dimensions of the disorder and has become a widely used standard measure. The first 5 items of the PDSS assess the core DSM-5-TR symptoms of panic disorder, and 2 additional items assess impairment in social and occupational functioning. Each item is scored on a 0 to 4 scale.

3.1.2.1. Handling of Missing PDSS Data

If individual items are missing from a given subscale of PDSS for an individual participant at a given time point, the subscale total will be calculated by prorating the total of non-missing items if the number of missing items is no more than one item of the total number of items in the subscale. The PDSS total score for an individual participant at a given time point will be similarly calculated by prorating the total of non-missing items if the number of missing items is less than or equal to 3. To prorate the value, the following formula is utilized:

$$P = \left(\frac{\sum_{i=1}^n j_i}{n} \right) U$$

Where n is the number of non-missing items, j_1-j_n represents the n non-missing values reported by the participant for the given subscale, and U is the number of total items in the given subscale.

If the number of missing items exceeds the specifications above, the subscale score or the total score for the individual participant at that time point will be considered missing.

3.1.2.2. Derivation of PDSS Total Score

The PDSS total score is defined as the sum of scores per participant per visit. The total score will range from 0 to 28 with higher scores indicating a higher severity of panic disorder.

3.1.3. Clinical Global Impression-Severity of Symptoms Scale

The global severity of panic disorder symptoms for each participant will be rated using the Clinical Global Impression Severity of Symptoms Scale (CGI-S) (Guy, 1976). The CGI-S scale is a 7-point scale that requires the clinician to rate the severity of the patient's illness at the time of the assessment relative to the clinician's experience with patients who have the same diagnosis. Raters select one response based on the following question: "Considering your total clinical experience with this particular population, how ill is the patient at this time?" Scores are 0=not assessed; 1=normal, not at all ill; 2=borderline ill; 3=mildly ill; 4=moderately ill; 5=markedly ill; 6=severely ill; and 7=among the most extremely ill patients. Participants with a score of 0 will be set to missing in the derived dataset.

3.1.4. Hamilton Anxiety Rating Scale

The Hamilton Anxiety Rating Scale (HAM-A) (Hamilton, 1959) is a clinician interview-administered scale designed to measure the signs and symptoms of anxiety states in an adult population. It has 14 items and a recall period of the past week. There are 2 domains covered within the questionnaire, a Somatic factor (made up of 8 items including somatic muscular, somatic sensory, cardiovascular symptoms, respiratory symptoms, gastrointestinal symptoms, genitourinary symptoms, automatic symptoms and behavior) and a Psychic factor (made up of 6 items including anxious mood, tension, fears, insomnia, intellectual and depressed mood). Each item is scored on the following scale: 0=Not Present, 1=Mild, 2=Moderate, 3=Severe, and 4=Very Severe. A total score (ranging from 0 to 56) can be calculated in addition to the 2-dimension scores. If more than 3 individual items are missing per domain, the HAM-A total score will not be calculated and will be left as missing. If less than or equal to 3 individual item scores are missing, the missing item scores will be imputed by the mean of all other available item scores, or the maximum possible values for the missing responses, whichever is smaller, to calculate the HAM-A total score. Lower scores indicate less anxiety.

3.2. Safety Assessments

3.2.1. Adverse Event

Adverse Events (AE) is defined as any untoward medical occurrence in a patient or clinical trial participant, temporally associated with the use of trial intervention, whether considered related to the trial intervention. NOTE: Signs and symptoms and/or abnormal laboratory test results indicating a common underlying pathology/diagnosis should be reported as a single AE.

All adverse events will be recorded on the ADVERSE EVENTS eCRF. Adverse events with missing severity will have the severity imputed as toxicity 'Grade 3' for the AE tabulations. Adverse events with missing relationship to IMP will have the relationship imputed as 'Related' for the AE tabulations if the AE started on or after the first dose of IMP. However, in the data listings these missing severity and/or relationship will be presented as missing.

3.2.1.1. Adverse Event of Special Interest

AESIs are defined as any event meeting the following criteria:

- AEs that result in the discontinuation of IMP
- AEs potentially related to abuse (refer to the Abuse Potential Monitoring Plan [APMP] document for details)
- AEs of suicidality
- C-SSRS (Since Last Visit) “Yes” answer to Suicidal Ideation Items #4 or #5 or any Suicidal Behaviors
- Corrected QT values using Fridericia's method (QTcF) >500 ms or an increase >60 ms from Baseline
- Liver enzymes:
 - ALT or AST $\geq 3 \times$ Upper Limit of Normal (ULN) and serum bilirubin $\geq 2 \times$ ULN (suspected Hy's Law)
 - ALT $\geq 5 \times$ ULN
- Hematologic abnormalities:
 - Absolute neutrophil count $< 1.5 \times 10^9/L$
 - Platelet count $< 100 \times 10^9/L$
 - Hemoglobin < 10 g/dL

These events will be noted by the investigator in the ADVERSE EVENT/ADVERSE EVENT OF SPECIAL INTEREST eCRF.

